1. INTRODUCTION

The pivotal Phase 3 POLAR program, studying calmagafodipir for the prevention of chemotherapy induced peripheral neuropathy, consists of two studies: POLAR-A and POLAR-M.

- POLAR-A is a placebo controlled, randomised (1:1) Phase III study of calmagafodipir 5 µmol/kg in combination with mFOLFOX6 compared to placebo+mFOLFOX6 in patients with adjuvant treatment of stage III or high-risk stage II colorectal cancer.
- POLAR-M is a placebo controlled, randomised (1:1:1) Phase III study of calmagafodipir in two different doses, 2 µmol/kg and 5 µmol/kg in combination with mFOLFOX6 compared to placebo+mFOLFOX6 in patients with metastatic CRC.

Patient recruitment in the POLAR-A and POLAR-M studies was initiated in late 2018 with the first patient randomised in on January 15, 2019, in POLAR-A and on POLAR-M on January 21, 2019.

On January 23, 2020, the Sponsor announced that the US Food and Drug Administration (FDA) had issued a clinical hold in the US of the POLAR program. The implication was that recruitment and dosing of patients in the POLAR-M study was halted in the US. Based on the evaluation of the independent Drug Safety Monitoring Board (DSMB), the Sponsor's position was that the overall safety profile for PledOx supported the continuation of the POLAR program and both studies continued as planned in Europe and Asia with dosing and further recruitment.

On March 1, 2020, the Sponsor decided to place recruitment and dosing of patients in the POLAR program on hold. The decision followed interactions with the French regulatory authority, ANSM, and the clinical hold issued by the US Food and Drug Administration (FDA) earlier in the year and was due to 4 observed events related to seizure. The Sponsor maintained its position that these events are not related to calmagafodipir, a position which was also supported by the DSMB and an additional independent external evaluation of these cases.

On April 6, 2020, the Sponsor decided to close the POLAR program early with a data cut-off targeted for the third quarter 2020 (further detailed later in this document). The decision was taken after a recommendation from the DSMB to stop the studies due to an accumulation of severe allergic reactions, primarily observed after repeated dosing.

Based on the development of the POLAR studies, a re-assessment of the sample size assumptions is needed to determine a reasonable statistical approach to the analysis of the POLAR studies.

The POLAR studies were designed based on the following sample size assumptions:

- POLAR-A: With 112 patients per group, the POLAR-A study has 91% power to detect a reduction (improvement) from 40% to 20% (OR = 0.375) in the primary endpoint using two-sided test controlled at the 0.05 type-I error rate. To account for 20% dropout in the study, in total 280 patients (140 patients per arm) will be randomised.
- POLAR-M: With 112 patients per group, the POLAR-M study has 91% power to detect a reduction (improvement) from 40% to 20% (odds ratio = 0.375) in the primary endpoint using two-sided test controlled at the 0.05 type-I error rate. To account for 20% dropout in the study, in total 420 patients (140 patients per arm) will be randomised.

Table 1: Patient disposition in the POLAR studies

	POLAR-A	POLAR-M	Total
Number of patients randomised	301	290	591
Number of patients dosed with ≥ 1 cycle of IMP	297	285	582
Number of patients dosed with ≥ 6 cycles of IMP	257	194	451
Number of patients dosed with ≥ 12 cycles of IMP	107	98	205

A total of 591 patients was randomised in the POLAR program and 582 patients dosed, of which 451 patients completed 6 cycles and 205 patients completed 12 cycles (see Table 1).

There are two main contributing factors to take into account when designing a reasonable statistical approach to the analysis of the POLAR studies:

- 1) POLAR-M only randomised 290 out of the planned 420 patients. This, together with the reduced dosing of patients (see bullet 2 below) means a separate primary analysis based on this data set cannot be supported.
- 2) Due to the Sponsor's decision to place the dosing of patients on hold on March 1, 2020, not all patients have had sufficient dosing of IMP to expect the full treatment effect of active treatment as assumed in the sample size calculation.

Taking these two aspects into consideration account (the fewer number of randomised patients and the reduced dosing of patients) a reasonable statistical approach is to conduct a combined primary analysis across the two studies, with the data from the two studies regarded as strata, based on a modified ITT analysis set defined by the eligibility of dosing with IMP as intended in the clinical study protocol. In addition, a standalone analysis of the primary endpoint in the fully recruited POLAR-A study will be conducted if the combined analysis is statistically significant. This approach will be further detailed in this document.

All analyses will be provided using the combined data from the two studies. However, both POLAR studies will also be analysed and reported separately.

This SAP is based on protocol versions 7.0/8.0 dated 09JAN2020/17APR2020 and will cover both POLAR-A, POLAR-M and the combined analyses across studies. The SAP will be reviewed at the blind review of the data before database lock and will be finalised before breaking the blind and database lock.

The table, listing and figure shells will be supplied in a separate document "POLAR – Statistical Output Specification".

The analysis and statistics reporting will be conducted at Binomial Sweden AB using SAS version 9.4.

2. STUDY OBJECTIVES AND DESIGN

2.1 POLAR-A

2.1.1 Primary Objective

The primary objective of the study is to compare PledOx (5 $\mu\text{mol/kg}$) vs placebo with respect to the proportion of patients with moderate or severe chronic CIPN.

2.1.2 Secondary Objectives

The secondary objectives of the study are to compare PledOx vs placebo regarding the following:

Efficacy

- The proportion of patients with mild, moderate or severe chronic CIPN
- The sensitivity to touching cold items
- The cumulative dose of oxaliplatin during chemotherapy
- The vibration sensitivity on the lateral malleolus
- The worst pain in hands or feet
- The functional impairment (in the non-dominant hand)
- The sustained efficacy on prevention of CIPN during long-term follow-up

Safety

- DFS
- Safety and tolerability

2.1.3 Exploratory Objectives

The exploratory objectives of the study are to compare PledOx vs placebo regarding the following:

- Chronic CIPN by supporting analysis using the full Functional Assessment of Cancer Therapy/Gynecologic Oncology Group-Neurotoxicity-13-item subscale (FACT/GOG-NTX-13)
- The cumulative dose of 5-FU during chemotherapy
- For both oxaliplatin and 5-FU: Dose intensity, number of cycles, dose reductions, reason(s) for dose reductions, patients with dose delays, and length of dose delays
- The functional impairment (in the non-dominant hand) during long-term follow-up.
- The worst pain in hands or feet during long-term follow-up
- QoL/health status
- Health economic impact

[figure not shown]
2.1.4 Study Design

POLAR-A is a Phase 3, multicenter, double-blind, placebo-controlled study using PledOx for prevention of chronic CIPN induced by oxaliplatin in patients with pathologically confirmed CRC, who are indicated for adjuvant mFOLFOX6 chemotherapy for up to 6 months.

Patients will be randomised in a 1:1 ratio to 1 of 2 treatment arms:

- Arm A: PledOx (5 μ mol/kg) + mFOLFOX6 chemotherapy
- Arm B: Placebo + mFOLFOX6 chemotherapy

Figure 1

$t=0$ (baseline: Day 1, Cycle 1); R=randomization; EoT=end of treatment; DFS=disease free survival

Note: CIPN will be evaluated by the first 4 items of the FACT/GOG-NTX-13 (i.e. FACT/GOG-NTX-4), targeting numbness, tingling or discomfort in hands and/or feet, also at 9, 12, 18 and 24 months after the first dose of IMP

2.2 POLAR-M

2.2.1 Primary Objective

The primary objective of the study is to compare each dose of PledOx (2 and 5 $\mu\text{mol/kg}$) vs placebo with respect to the proportion of patients with moderate or severe chronic CIPN.

2.2.2 Secondary Objectives

The secondary objectives of the study are to compare each dose of PledOx vs placebo regarding the following:

Efficacy

- The proportion of patients with mild, moderate or severe chronic CIPN
- The sensitivity to touching cold items
- The cumulative dose of oxaliplatin during chemotherapy
- The vibration sensitivity on the lateral malleolus
- The worst pain in hands or feet
- The functional impairment (in the non-dominant hand)
- The sustained efficacy on prevention of CIPN during long-term follow-up

Safety

- Overall response rate (ORR)
- Progression-free survival (PFS)
- Overall survival (OS)
- Safety and tolerability

2.2.3 Exploratory Objectives

The exploratory objectives of the study are to compare each dose of PledOx vs placebo regarding the following:

- Chronic CIPN by supporting analysis using the full FACT/GOG-NTX-13
- The cumulative dose of 5-FU during chemotherapy

[figure not shown]
- For both oxaliplatin and 5-FU: Dose intensity, number of cycles, dose reductions, reason(s) for dose reductions, patients with dose delays, and length of dose delays
- The pharmacokinetic (PK) profile of PledOx with multiple dosing (only at pre-selected sites and in 84 patients in total)
- The QT/QTc interval using a 12-lead electrocardiogram (ECG) only at pre-selected sites and in 84 patients in total)
- The functional impairment (in the non-dominant hand) during long-term follow-up
- The worst pain in hands or feet during long-term follow-up
- QoL/health status
- Health economic impact

2.2.4 Study Design

POLAR-M is a Phase 3, multicenter, double-blind, placebo-controlled study to establish the efficacious dose of PledOx in prevention of chronic CIPN induced by oxaliplatin. Patients with metastatic CRC, who are indicated for first-line modified FOLFOX-6 (mFOLFOX6) chemotherapy for at least 3 months, without any pre-planned treatment breaks, will be randomised in a 1:1:1 ratio, stratified by region (Asia, non-Asia) and PK sub-study (yes, no), to one of three treatment arms:

- Arm A: PledOx (2 μ mol/kg) + mFOLFOX6 chemotherapy
- Arm B: PledOx (5 μ mol/kg) + mFOLFOX6 chemotherapy
- Arm C: Placebo + mFOLFOX6 chemotherapy

Figure 2. POLAR-M Study Design

t=0 (baseline: Day 1, Cycle 1); R=randomization; EoT=end of treatment; PFS=progression-free survival; OS=overall survival; EoS=end of study

Note: CIPN will be evaluated by the first 4 items of the FACT/GOG-NTX-13 (i.e. FACT/GOG-NTX-4), targeting numbness, tingling or discomfort in hands and/or feet, also at 12, 15, 18, 21 and 24 months after the first dose of IMP

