3. GENERAL STATISTICAL PRINCIPLES

Testing Procedure. The formal testing procedure of the primary endpoint is first to perform the analysis on PledOx 5 µmol/kg vs Placebo on both POLAR-A and POLAR-M studies combined. If the results are statistically significant then the same analysis will be performed on the POLAR-A study alone. All tests will be done on the 0.05 level of significance.

Statistical analyses will include stratification factors for study (POLAR-A / POLAR-M) and region (Asia/non-Asia).

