5.1 Primary Endpoint

5.1.1 Moderate to Severe CIPN

The primary endpoint is defined as the proportion of patients (with moderate or severe chronic CIPN) scoring 3 or 4 in at least 1 of the first 4 items of the FACT/GOG-NTX-13 (i.e., FACT/GOG-NTX-4), targeting numbness, tingling or discomfort in hands and/or feet, 9 months after the first dose of IMP (i.e. PledOx or placebo administered on Day 1, Cycle 1 of mFOLFOX6 chemotherapy).

Baseline is defined as the time of administration of the first dose of IMP (Day 1, Cycle 1).

Moderate to Severe CIPN will derived (SAS) as follows:

```
cipn=0;  
IF ntx1_std=. AND ntx2_std=. AND ntx3_std=. AND ntx4_std=. THEN cipn=.;  
ELSE IF ntx1_std IN('3','4') OR ntx2_std IN('3','4') OR  
      ntx3_std IN('3','4') OR ntx4_std IN('3','4') THEN cipn=1;
```

Primary Analysis – Cochran-Mantel-Haenszel. The primary analysis of the primary endpoint Moderate to Severe CIPN (yes/no) at 9 months after first dose of IMP will be analysed by the Cochran-Mantel-Haenszel (CMH) estimate of the common relative risk of Moderate to Severe CIPN. The treatment effect will be assessed by estimating the ratio of the incidence rates of CIPN in PledOx 5µmol/kg versus Placebo along with its 95% confidence interval and corresponding p-value. The CMH estimate will be adjusted for cumulative exposure of oxaliplatin and stratified by study and region. Incidence rates (95% CIs) for each treatment will also be presented.

Notations. The combined analysis includes two studies (POLAR-A and POLAR-M) and two geographical regions (Asia/Non-Asia), and so there are 4 strata, where

- 1 = POLAR-A / Asia
- 2 = POLAR-A / Non-Asia
- 3 = POLAR-M / Asia
- 4 = POLAR-M / Non-Asia

Treatments are denoted by 1 and 2, where 1 = PledOx 5µmol/kg and 2 = Placebo. For treatment j in the i^{th} strata the cumulative exposure of oxaliplatin is T_{ij} and E_{ij} is CIPN events. Let $T_{i\bullet} = T_{i1} + T_{i2}$ and $E_{i\bullet} = E_{i1} + E_{i2}$ denote total cumulative exposure of oxaliplatin and total CIPN events in the i^{th} strata.

CMH point estimate of the common relative risk across strata. Under $H_0: R_1 = R_2 = R$, Breslow and Day [1] provide the stratified Cochran-Mantel-Haenszel estimate of the common relative risk as

$$\hat{R}_{M-H} = \frac{\sum_{i=1}^k \frac{E_{i1}T_{i2}}{T_{i\bullet}}}{\sum_{i=1}^k \frac{E_{i2}T_{i1}}{T_{i\bullet}}}$$

Also, Robins, Breslow and Greenland [2] provide an estimate of the variance of $\log \hat{R}_{M-H}$ as

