Supportive Analysis of the primary endpoint - Negative Binomial Regression. A supportive analysis of the primary endpoint Moderate to Severe CIPN (yes/no) at 9 months after first dose of IMP will be analysed by a negative binomial regression model adjusted for study (POLAR-A / POLAR-M) and region (Asia / non-Asia). An offset variable will also be used to adjust for the oxaliplatin exposure defined as the logarithm of the cumulative dose of oxaliplatin received by each patient. Estimate of the treatment contrast (rate ratio) and its corresponding 95% confidence interval will be based on the anti-log of the model parameter estimate and CI.

SAS Code Example Negative Binomial Regression using PROC GENMOD

```
PROC GENMOD;
  CLASS study region trt;
  MODEL cipn = study region trt/DIST=negbin LINK=log SCALE=deviance OFFSET=log_exp;
  ESTIMATE 'PledOx 5 µmol/kg vs Placebo' trt 1 -1;
  LSMEANS trt / CL EXP;
RUN;
```

If convergence criterion is not met using PROC GENMOD an alternative using PROC NLMIXED will be used.

SAS Code Example Negative Binomial Regression using PROC NLMIXED

```
PROC NLMIXED;
  PARMs b0 -2 b1 .1 b2 -.01 b3 .1 phi .1;
  eta = log_exp + b0 + b1*(study=1) + b2*(region=1) + b3*(trt=0);
  mu = exp(eta);
  LL = y*log(phi*mu) - (y+(1/phi))*log(1+(phi*mu)) + lgamma(y+(1/phi)) -
lgamma(1/phi) - lgamma(y+1);
  MODEL y ~ general(LL);
RUN;
```

Exploratory Analysis – Exact Logistic Regression. An exploratory analysis of the primary endpoint Moderate to Severe CIPN at 9 months after first dose of IMP will be analysed by exact logistic regression model adjusted for study (POLAR-A / POLAR-M) and region (Asia / non-Asia). Estimate of the treatment effect and its corresponding 95% confidence interval will be based on the odds-ratio.

SAS Code Example Exact Logistic Regression

```
PROC LOGISTIC DESC;
  CLASS study region trt(ref='0: Placebo');
  MODEL cipn = study region trt;
  EXACT trt;
RUN;
```

Using the same example data presented above, a crude estimate of the odds-ratio then is:

$$(0.27/0.73) / (0.41/0.59) = 0.53$$

Table 4 Example data: Exact Logistic Regression of Moderate to severe CIPN 9 months after first dose of IMP

	N	CIPN (%)	Odds-ratio	95% CI	P-value
PledOx 5 µmol/kg	118	27.1	-	-	-
Placebo	118	40.7	-	-	-
PledOx 5 µmol/kg vs Placebo	236	-	0.54	[0.31;0.94]	0.0293

Data Presentations

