6.10 Progression-Free Survival (POLAR-M only)

Endpoint. Progression-Free Survival (PFS) is defined as the time from the date of randomisation until the date of objectively determined PD (according to RECIST v1.1) or death due to any cause. Patients without objectively determined PD who are alive at the end of the follow-up period (or who were lost to follow up) will be censored on the date of the patient's last complete radiographic tumor assessment. If no baseline or post-baseline radiologic assessment is available, the patient will be censored at the date of randomisation.

Cox Proportional Hazards Model. Time (number of days) from randomisation to event or censoring will be analysed by a cox proportional hazards model using region (Asia / non-Asia) and Treatment as fixed factors in the model. The hazard ratio along with its 95% confidence interval of the PledOx doses compared to placebo will be estimated.

Data presentations

- Table: Progression-free survival based on the cox proportional hazards model will be presented by the number and percentage of events (N, %), Hazard Ratio (95% CI), Minimum, Q1, Median, Q3 and Maximum time to event or censoring by treatment group and total.
- Figure: Progression-free survival will be depicted graphically by a Kaplan-Meier plot by treatment group.

All PFS data will be listed by patient.

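### POLAR-M was randomised within PK sub-study as well as region, but no analysis includes PK sub-study; the effect on the primary test is essentially nil and the repair is simple

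*SAP*

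**What the plan says.** Section 2.2.4 describes the POLAR-M allocation: patients "will be randomised in a 1:1:1 ratio", "stratified by region (Asia, non-Asia) and PK sub-study (yes, no". That gives four randomisation cells. Section 2.2.3 gives the planned size of the sub-study: "only at pre-selected sites and in 84 patients in total".

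The analysis factors are set in Section 3: "Statistical analyses will include stratification factors for study (POLAR-A / POLAR-M) and region (Asia/non-Asia". The later sections follow this:

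- **Primary analysis, Section 5.1.1:** "The CMH estimate will be adjusted for cumulative exposure of oxaliplatin and stratified by study and region". The plan counts the strata explicitly: "two geographical regions (Asia/Non-Asia), and so there are 4 strata". Sections 5.3.1 and 5.3.7 use the same method.
- **Supportive and exploratory analyses, Section 5.1.1:** a "negative binomial regression model adjusted for study (POLAR-A / POLAR-M) and region (Asia / non-Asia", and an exact logistic model with the same two factors.
- **ANCOVA and ANOVA, Sections 5.3.2 to 5.3.6, 5.4.2 to 5.4.4 and 5.4.7 to 5.4.9:** study, region and treatment, with the baseline value in the ANCOVA models.
- **Exact logistic regression for pain, Section 5.4.10:** study and region.
- **POLAR-M PFS and OS, Sections 6.10 and 6.11:** Cox models "using region (Asia / non-Asia) and Treatment as fixed factors in the model".

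PK sub-study is in none of them.

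**The concern.** The usual principle is that an analysis reflects the factors on which randomisation was restricted. Here one of two factors is kept and the other is left out, and the SAP gives no reason.

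Two things could be at stake. If sub-study membership is related to outcome, a linear model that omits it carries that variation in its residual and loses a little precision. If the arms are no longer balanced within sub-study cells in the patients actually analysed, an analysis that pools over those cells has no protection against the resulting confounding.

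**Working it through.** **1. The plan's own example.** In the Section 5.1.1 formulas, let the active arm hold the same share *a* of the oxaliplatin exposure in every stratum, so T_i1 = a·T_i and T_i2 = (1−a)·T_i. Write E1 and E2 for total events on active and placebo, and E = E1 + E2. Then

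- R = [(1−a)/a] × E1/E2
- V[log R] = ((1−a) + aR)² / (R·a(1−a)·E)
- substituting R gives V = E/(E1·E2) = 1/E1 + 1/E2.

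The example in Tables 2 and 3 has 32 and 48 events and a ratio of 0.6869. So V = 1/32 + 1/48 = 0.05208 and SE = 0.2282. The interval is 0.6869 × exp(±1.96 × 0.2282) = 0.4392 to 1.0744, with p = 0.0998. Table 3 gives 0.4391 to 1.0745 and p = 0.0999, so the reduced form reproduces the plan's figures to within rounding.

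**2. What this means for the strata.** Neither R nor V depends on how the patients are divided into strata, provided the exposure share is the same in each. Stratified randomisation makes that roughly true. Going from 4 to 6 strata then changes nothing in the primary test.

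**3. Simulation.** The SAP formulas were run 40,000 times per scenario with 4 strata (study by region) and 6 strata (POLAR-M also split by sub-study). These inputs are assumptions, not in the SAP:

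- 150 patients per arm in POLAR-A and 97 in POLAR-M, 25% in Asia
- 84/3 = 28 sub-study patients per POLAR-M arm
- equal mean exposure and exact balance within cells
- placebo rate 40%, rate ratio 1 or 0.675
- sub-study rate shifted by −20 to +20 points.

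| Variance | Quantity | 4 strata | 6 strata |
|---|---|---|---|
| SAP formula | Rejection under null | 0.009–0.012 | identical |
| SAP formula | Power | 0.714–0.776 | identical |
| Binomial Mantel-Haenszel | Rejection under null | 0.047–0.051 | 0.048–0.051 |
| Binomial Mantel-Haenszel | Power | 0.836–0.895 | 0.838–0.897 |

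Within a scenario the binomial version moved by about 0.2 points at most, and the mean estimated ratio agreed to four decimals. The null rate near 1% comes from the SAP's exposure-based variance and is the same with either stratification.

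**4. Linear models.** The share of POLAR-M outcome variance that a two-level factor explains is q(1−q)d², where q is the sub-study share and d the shift in SD units. Neither the enrolled share nor d is stated. Take q between 84/420 = 0.20 (planned) and 84/290 = 0.29 (if all 84 were enrolled), and assume d² = 0.15²/0.24 = 0.094, a shift of about 0.3 SD. The share is then 0.16 × 0.094 = 1.5% to 0.206 × 0.094 = 1.9%. POLAR-M standard errors would fall by about 0.8% to 1.0%, and less in the combined data. If d = 0 there is no gain.

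**5. Where balance may fail.** Steps 1 to 3 rest on equal exposure shares. Randomisation supports that for all randomised patients. The mITT rules in Section 3.1 select partly on later events (a post-baseline efficacy assessment, the 3-month visit, the sixth IMP cycle). Section 5.2 includes an observed-case version, and the divisor is oxaliplatin exposure received. Any of these can make the active share differ between sub-study and other patients. If the CIPN rate also differs between them, the 4-stratum ratio absorbs that difference and the 6-stratum ratio does not. The simulation imposed exact balance and so does not measure this.

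**The case against.** The case for leaving the plan alone is strong on size. The primary test does not change under balance, and omitting a balanced factor causes no bias. The factor looks administrative, and nothing in the SAP suggests that it predicts CIPN. Splitting further also thins the data: of 84 planned sub-study patients, 2 × 28 = 56 fall in the two arms compared, before the split by region, the mITT exclusions and missing 9-month data. All of that stands. It limits the size of the point but does not remove it, because balance is not assured in the analysed set and the Mantel-Haenszel estimator tolerates sparse strata.

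A reader might infer more than the SAP supports:

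- **That the primary standard error is too large by a calculable amount.** Setting 0.2 × 0.8 × 0.15² = 0.0036 against a binomial variance of 0.24 gives 1.5%. The primary analysis does not use a binomial variance, so the figure does not apply to it.
- **That every model would gain precision.** In Cox and logistic models, adding a prognostic covariate changes the conditional estimand and does not in general shrink the standard error.
- **That Section 2.5 should have listed the omission.** That section lists changes from the protocol's analysis. The protocol is not at hand, so it cannot be said that anything changed.
- **That the sub-study marks a separate group of centres.** Section 3.1 describes a subset of patients at pre-selected sites across all regions. Other patients may have been treated at the same sites.

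**Conclusion.** The point holds as a minor one. The SAP states two randomisation factors for POLAR-M and uses only one of them. The primary CMH test is essentially unaffected: exactly so when exposure shares are equal across strata, and by about 0.2 points of power or type I error even under a binomial variance with a 20-point rate difference. The possible benefits are about 1% off POLAR-M standard errors in the ANCOVA and ANOVA models, if the factor is moderately prognostic (an assumption), and protection of unknown size against imbalance within sub-study cells. The SAP gives no ground for calling the primary result biased or invalid.

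**What to change.** Split the two POLAR-M strata in Section 5.1.1 by PK sub-study, giving 6 strata in the combined analysis and 4 in POLAR-M alone. The formulas stay as they are. Add the factor to the negative binomial, exact logistic, ANCOVA and ANOVA models, and to the POLAR-M Cox models in Sections 6.10 and 6.11, on the ground that the analysis follows the randomisation strata. In the combined models, code all POLAR-A patients as not in the sub-study; the study term keeps the two trials apart. Amend the general statement in Section 3 to match.

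The cost is one variable already needed for randomisation and some sparse Asia sub-study cells. A stratum with no exposure in one arm contributes nothing to the Mantel-Haenszel sums, and the SAP should say so. Section 1 has the SAP finalised before unblinding, so the change should be made by then.
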